- **Short Form-12:** The SF-12 is a self-administered, generic HRQOL measure derived from the Rand Health Insurance Long Form. The SF-12 is validated for the U.S. with age and gender normal values. This instrument provides mental and physical component scales (MCS, PCS) for translating health status and changes in health status between cohorts of patients with distinct disorders. Previous studies in adult scoliosis have used the SF-12 to measure HRQOL.

All three of these outcomes instruments will be available in Spanish. The Spanish translated HRQOLs have been validated.

**Progress & Satisfaction questionnaire.** This is a brief, four item questionnaire for the patient to document satisfaction with treatment and treatment assignment. This questionnaire will be completed at the time of the office visit or by mail. The questionnaire is also completed at the time of crossover and prior to any revision surgery.

**Functional Treadmill test:** All patients will have a standardized functional treadmill test performed at baseline and 2 years post-treatment. This test is performed routinely at Washington University and has been published in *The Journal of Bone & Joint Surgery*. (See Appendix for details).

If a Non-Surgical patient crosses over to the Surgical arm and tentative surgery date is prior to 21 month follow up, 2 year post intervention treadmill test will be delayed until the patient is 2 year s/p *CROSSOVER surgical procedure*.

If Non-Surgical patient crosses over to Surgical arm and tentative surgery date is between 21 and 30 month follow up, post intervention TM will be obtained prior to crossover surgery. These patients will be asked to complete a 3rd treadmill test 2 years after CROSSOVER surgical procedure. If the patient is agreeable, a separate, supplemental consent will be obtained for 3rd treadmill test. Patient and site (physical therapist) will be reimbursed for all three treadmill tests.

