Statistical Analysis Plan

Study Design Overview: This is a Phase III Clinical Trial. Our overall goals are to evaluate the effectiveness of nonoperative and operative interventions in patients with adult symptomatic lumbar scoliosis (ASLS) and to identify important clinical and radiographic determinants of change in patient-reported HRQOL. To accomplish these goals, a 5-year cooperative, multi-center longitudinal randomized study with a concurrent observational cohort is proposed.

Specific Aim #1: Compare the outcomes of surgery and nonoperative treatment in patients aged 40 to 80 with ASLS defined as a lumbar curve with a coronal Cobb measurement of 30° or more, and either of the following: Oswestry Disability Index (ODI) score of 20 or more; or Scoliosis Research Society Quality of Life (SRS-QOL) instrument score of 4.0 or less, in the domains of pain, function and/or appearance.

Null Hypothesis: Nonoperative and operative treatment groups will have similar outcomes at follow-up.

Specific Aim #2: Evaluate the impact of patient factors (age, gender, socioeconomic status, education) and comorbidities [mental health, body mass index (BMI) and bone mineral density (BMD)] on adverse events and treatment outcomes for both the non-operative and operative arms. Incorporate these variables into a prediction model to help identify those patients most likely to benefit from either a surgical or non-operative approach.

Hypothesis: Age, gender, socioeconomic status, education, and comorbidities will have an impact on the final result at 2-4 years post-intervention.

1.6 Statistical Analysis. The primary analyses will use longitudinal regression modeling (Using SAS 9.4 and the Mixed procedure for continuous and the GLIMMIX procedure for categorical outcomes), where outcomes being assessed will be change from baseline and the primary covariate will be the baseline outcome score. These longitudinal modeling techniques that incorporate various baseline covariates, such as baseline outcome, patient age, gender, and other patient- and treatment-specific factors will allow evaluating of both differences in change from baseline 1. Across time of assessment by treatment groups adjusted for baseline covariates and 2. Treatment group differences at any specified point of time.

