Addendum 8/29/12: (modified and edited 6/19/13) The primary analysis plan for this study is to first evaluate the RCT and OBS studies separately using mixed model longitudinal regression analysis using an intent-to-treat approach. As was done in the SPORT analysis, assessment Intervals are treated as a fixed effect, meaning with each interval developed based on the date of intervention. Data gathered prior to date of intervention (DOI) will be considered baseline and fixed data points gathered after DOI will be classified according the form designation (e.g., 3mo, 6mo). Data points gathered after DOI that were not fixed points (e.g., complications, severe adverse events) will be associated with a fixed interval based on the length of time from the data point and DOI. A second random effects variable (Delta) will be created within each interval that reflects the distance (no. of days) between the actual observed point and the center of the fixed interval that this point falls within. Thus, patients may have multiple data points within a fixed interval and the distance orTime of data collection relative to DOI within each fixed interval will be included in the model. In addition, a Delta random variable, defined as the distance between the center of the fixed interval and the Time of data collect will, also be created. The primary analysis will regress the change in outcome (eg for the pcs outcome d_pcs) on baseline pcs (b_pcs), treatment, interval, site and patient age and sex,

For the RCT cohort, the base model for PCS would be

$$d_{\text{pcs}} = b_{\text{pcs}} \text{ treatment} | \text{interval} | \text{time site age sex}$$

A secondary analysis will replace time with the Delta variable with the model forcing the Delta covariate to have a value of 0 – thereby adjusting the results to reflect the expected value for the outcome as if the outcome was assessed at the exact center of the fixed interval.

$$d_{\text{pcs}} = b_{\text{pcs}} \text{ treatment} | \text{interval} \text{ delta site age sex} \text{ delta / delta} = 0$$

Where:

T_DOI = Date dependent variable was collected – DOI WITH negative T_DOI values indicating outcomes being assessed prior to treatment and positive T_DOI values indicating the time after DOI that the outcome was evaluated. Note that T_DOI values are nested within d_pcs
= -pcs-b_pcs (a positive change would reflect improvement)

b_pcs = baseline pcs

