Treatment = is a fixed effect with 2 levels the operative or non-operative care of the patient

Interval = is a fixed effect with X levels (depending on the outcome) indicating the follow-up times for collected patient outcomes

Time = The number of days between the date of assessment within an interval and the date of Intervention

site = the study site enrolling the patient (note site interactions may not be estimable in which case the interaction effects with site would be removed from the model)

age = a preplanned covariate

sex = a preplanned covariate

delta = a random effect reflecting the distance (in days) of the observed score in an interval from the center of the interval

Comparing the differences in these two modeling approaches may be useful for evaluating the relative merits of the two analysis approaches.,

For predictive modeling crossover will not be considered and as “Intent to treat” modeling – where the assigned treatment (in the RCT) or the selected treatment (in the OS) cohorts will be retained throughout the analysis.

Additional baseline covariates may be added to this model depending on the results of preliminary comparison of baseline differences between treatment groups and recursive partitioning methods will explore additional possible baseline factors and interactions among these factors to detect patient profiles that vary across treatment assignment. In addition, significant relationships between baseline variables and crossover status and loss to follow-up will also be useful for identifying covariates.

For the OBS group, where baseline differences between the two treatment groups are expected, the same basic model will be used and the same approach for adding covariates to the model based baseline differences between treatment groups, crossover status and loss to follow-up will be used.

The primary hypothesis of interest concerns differences between treatment outcomes at each time interval and differential change in outcomes within treatment across time intervals. Thus, preplanned follow-up simple effects tests associated with the treatment x interval interaction will be explored even if the interaction itself is not statistically significant (this is what preplanned means).

These simple effects tests will evaluate:

1. Differences in effect size (e.g. d_pcs) at each interval between the two treatment groups (e.g., are the effect sizes between treatment groups at 2 years significantly different?);

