Treadmill evaluation. Again, longitudinal mixed model regression analysis will be used to evaluate the treadmill evaluation. However, since crossover to surgery will trigger a “new” baseline treadmill test, these patients will be repeated in the analysis with their 2nd baseline considered their follow-up treadmill test relative to the 1st baseline score and their final treadmill test 2 years following their 2nd baseline treadmill test will be considered their follow-up treadmill test relative to their 2nd baseline treadmill test.

Treadmill = treatment | interval| time site age sex

Treadmill = treatment | T_DOI(interval) site age sex

Patients who crossed over to surgery will be provided with a second DOI value (DOI_cNS) that will be used in conjunction with the date of the follow-up treadmill test to define the delta associated with the 2 year interval data form used to gather the follow-up treadmill score.

Addendum 1/17/13: Sample Size Calculation.

A sample size of 82 patients (41 per treatment arm) was estimated to provide 80% power with an SRS-22 effect size of ≥ 0.714 , 10% loss-to-follow-up at 2 years postoperative, and 20% crossover from nonoperative to operative intervention, based upon a mixed-model longitudinal analysis accounting for repeated measures at follow-up. A priori sample size estimations require estimates of outcome variances that may be inaccurate in the actual population studied. To account for this a bootstrap sample size estimation using data from the first 26 patients randomized was performed to provide a more accurate assessment of the required sample size needed to address the original trial aims, to include both the SRS-QOL and ODI.

Sample Size Estimation

Interval	ODI Power	SRS Power	n/GRP
3 months	0.0390	0.6770	18
6 months	0.7270	0.9980	
9 months	0.5600	1.0000	
12 months	0.8170	0.9950	

These results suggested that >80% power could be achieved to address Aim #1 with 36 randomized patients (18 patients per group).

Enrollment in the Observational cohort closed May 2013. Enrollment in the randomized cohort closed July 2014 with 63 participants, 70% of the original enrollment goal, this enrollment goal was felt, based on the above sample size analyses, to allow for sufficient power making allowances for loss to follow-up and cross-over over time.

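### Neither printed treadmill model includes the baseline treadmill score, and the SAP does not say how that score enters, so the 2-year contrast is less precise than a baseline-adjusted one

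*SAP*

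**What the plan says.** The Treadmill evaluation paragraph of the SAP addendum dated 8/29/12 (modified 6/19/13) gives two models: "Treadmill = treatment | interval| time site age sex" and "Treadmill = treatment | T_DOI(interval) site age sex". In both, the response is the treadmill score, not a change, and no baseline treadmill term appears on the right.

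The baseline value is scheduled. Protocol 1.5.1, Functional Treadmill test: "All patients will have a standardized functional treadmill test performed at baseline and 2 years post-treatment".

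Elsewhere the SAP handles baseline explicitly. Section 1.6, on the primary analyses: "outcomes being assessed will be change from baseline and the primary covariate will be the baseline outcome score". The same addendum applies this rule to the SF-12 physical score: "The primary analysis will regress the change in outcome (eg for the pcs outcome d_pcs) on baseline pcs (b_pcs), treatment, interval".

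The text on how baseline enters the treadmill model points in different directions. On crossover patients, the paragraph has the "2nd baseline considered their follow-up treadmill test relative to the 1st baseline score". The addendum allows for "negative T_DOI values indicating outcomes being assessed prior to treatment", which could make a pre-treatment test a response row. But its list of terms says "Interval = is a fixed effect with X levels (depending on the outcome) indicating the follow-up times for collected patient outcomes", and it treats data gathered before the intervention date as baseline.

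**The concern.** The baseline value of an outcome is usually its strongest predictor, and SAP 1.6 itself attributes most of the expected shrinkage in standard deviation to it. The treadmill has one scheduled follow-up test, so there is no run of repeated measures to recover lost precision. The randomised cohort closed at 63 participants.

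There are two consequences. First, precision is given up although the data that would supply it are already scheduled. Second, the notation leaves the estimand open: two analysts could fit different models in good faith and report different 2-year treatment differences. The addendum promises a p-value for each outcome at 12 and 24 months, so the choice should be fixed before the data are analysed.

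**Working it through.** **Inputs from the documents.** Tests at baseline and 2 years (Protocol 1.5.1); 63 randomised and 10% loss at 2 years (SAP Addendum 1/17/13); 1:1 allocation (Protocol 1.3); two-sided 0.05 (SAP 1.6.2). The effect of 0.714 SD is stated for the SRS score and is used here only as an illustration.

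**Assumptions.** The documents give no treadmill SD and no baseline to 2-year correlation r. I range r from 0.3 to 0.8, with equal SDs at both times and in both arms. The other covariates are ignored.

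**Check of the method.** The plan has no treadmill power figure to reproduce. A two-sample t-test calculation reproduces all six sample sizes in SAP Table 2 (24, 37, 64, 32, 50, 87).

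**What each reading estimates.**
- *Baseline unused:* a difference in raw 2-year scores.
- *Baseline as a level of interval:* each arm has its own free baseline mean. The 2-year simple effect is then the raw 2-year difference, and the treatment by interval contrast is the change-score difference. A mixed model fitted to one simulated data set confirmed both (0.535 and 0.535; 0.229 and 0.229).
- *Baseline subtracted:* the change-score difference.

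**Precision.** In units of the score variance, the contrast variances are proportional to 1 (raw), 2(1−r) (change) and 1−r² (baseline-adjusted). Relative to the adjusted contrast:
- raw: 1/(1−r²). At r = 0.5, 1/0.75 = 1.33; at r = 0.7, 1/0.51 = 1.96.
- change: 2(1−r)/(1−r²) = 2/(1+r). At r = 0.5, 2/1.5 = 1.33; at r = 0.7, 2/1.7 = 1.18.

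Both exceed 1 for every r between 0 and 1.

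Patients per arm at 2 years: 63 × 0.9 / 2 = 28.35. Power for a 0.714 SD effect:

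| r | raw/adjusted variance | change/adjusted variance | power, raw | power, change | power, adjusted |
|---|---|---|---|---|---|
| 0.3 | 1.10 | 1.54 | 75.2% | 60.7% | 78.3% |
| 0.4 | 1.19 | 1.43 | 75.2% | 67.4% | 81.5% |
| 0.5 | 1.33 | 1.33 | 75.2% | 75.2% | 85.6% |
| 0.6 | 1.56 | 1.25 | 75.2% | 83.9% | 90.5% |
| 0.7 | 1.96 | 1.18 | 75.2% | 92.6% | 95.6% |
| 0.8 | 2.78 | 1.11 | 75.2% | 98.7% | 99.2% |

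**Baseline difference.** Let the arms differ by D at baseline, with follow-up regressing on baseline with slope r and no treatment effect. The raw contrast then has expectation rD, the change contrast −(1−r)D and the adjusted contrast 0. For an assumed D of 0.3 SD:
- r = 0.5: raw 0.15, change −0.15. Simulated means (28 per arm, 1,500 runs): 0.153, −0.153 and, adjusted, −0.002.
- r = 0.7: raw 0.21, change −0.09. Simulated means: 0.204, −0.091 and, adjusted, −0.004.

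**The case against.** The strongest reply is that the SAP does not ignore baseline. The treadmill paragraph refers back to the longitudinal mixed model, speaks of a follow-up test relative to a baseline score, and uses a time variable that can be negative. With one scheduled follow-up, an interval factor has a single scheduled level unless baseline is another. SAP 1.6 also states the baseline-covariate rule for the primary analyses generally. For the observational cohort, Stage 3 commits to covariate adjustment, and the addendum lets covariates be added where the groups differ.

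Much of this stands. It rules out saying that the plan discards baseline. It does not supply the missing term. The remark about a score relative to baseline concerns crossover patients, the definition of interval points the other way, and the extra covariates are discretionary and not tied to the treadmill score.

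A reader might infer that the comparison keeps any baseline difference in full. The documents do not support that. It needs the raw-score reading, and even then only about an r-sized share remains; a change contrast subtracts the difference. In the RCT such a difference is chance, not systematic bias.

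A reader might also merge the precision losses into one range, such as 15% to 49% of patients discarded. That mixes two models: at r of 0.5 to 0.7 the loss is 25% to 49% for raw scores (r² = 0.25 to 0.49) and 25% to 15% for change scores ((1−r)/2 = 0.25 to 0.15).

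Finally, in a non-randomised cohort the choice between change scores and baseline adjustment is a recognised judgement, since each rests on different assumptions. That is fair, and it is a reason to state the choice.

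**Conclusion.** The point holds as an unresolved specification that costs precision. Both printed formulas lack the baseline treadmill term that the SAP's own approach would include, and the text does not decide among the three readings. The direction of the precision loss depends on neither the reading nor the exact r, provided r lies between 0 and 1. Its size depends on both: at an assumed r of 0.5 to 0.7 the variance ratio is 1.33 to 1.96 for raw scores and 1.33 to 1.18 for change scores.

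Carry-over of a baseline difference is conditional on the raw-score reading. It matters mainly in the observational cohort, where SAP Stage 3 expects the groups to differ at baseline.

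The consequence is limited to a non-primary outcome. The primary outcome is change in the SRS-QOL subscore; its analysis and sample size are unaffected.

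**What to change.** 1. Define the treadmill response explicitly and replace both formulas with the form used for the other outcomes: d_treadmill = b_treadmill treatment site age sex, plus a term for the actual test date. Once b_treadmill is in the model, using the change or the 2-year score as the response gives the same treatment coefficient.
2. In the RCT, a model with baseline as a response row and a common baseline mean across arms is an acceptable alternative. Free baseline means by arm would not recover the precision.
3. State which baseline pairs with which follow-up test for crossover patients. The SAP enters these patients twice, with a second baseline at crossover. Protocol 1.5.1 delays the 2-year test for those crossing over before 21 months, and describes a test before surgery and a third test only for those crossing over between 21 and 30 months. These passages must be reconciled before the records can be paired.

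Items 1 and 2 cost SAP wording only, because the baseline test is already scheduled for every patient. Item 3 also needs a check of which tests exist for each crossover patient.

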b. Variable Transformations: Transformations will be employed as needed to produce variables that conform to the distributional assumptions underlying the regression models that will be used. For example, some variables may be transformed to the logarithm scale for analysis, to reduce any marked positive skew; in these cases, results will be reported on the original scale of the variable to aid in interpretation.

Transformations may also be required to ensure additivity of variable effects in general linear models (for example, the outcome may be a quadratic rather than a linear function of age).

Stage 3 – Inferential Analysis:

Specific Aim 1: Compare the outcomes of surgery and non-operative treatment in patients aged 40 to 80 with ASLS defined as a lumbar curve with a coronal Cobb measurement $\geq 30^\circ$ and either of the following: Oswestry (ODI) score of 20 or more, or Scoliosis Research Society Quality of Life instrument (SRS-QOL) score of 4.0 or less in the domains of pain, function and/or appearance.

a. Primary Analyses: All the data analyses required to fulfill the specific aims of the study will be accomplished using statistical methods for repeated measures and longitudinal data using the SAS system's MIXED and GLIMMIX procedures for continuous and categorical outcomes, respectively. These procedures use maximum likelihood methods to estimate variances associated with the fixed and random effects of the model. In the randomized cohort, the primary analysis will be on an intent-to-treat basis. For the observational cohort, differences between treatment groups are expected at baseline and these will be controlled for by using covariate adjustment within the longitudinal regression models. We will model each HRQOL measure as the change at follow-up from baseline at each study month (i.e., at 3, 6, 12, 18, 24, 30, 36, 42, and 48 months), adjusting for baseline level while clustering the vector of outcomes within patients. Results will provide estimated means and standard deviations for the rate of change over the 12-month and 24-month (primary endpoint) follow-up periods, (1) assuming a linear rate of change, and (2) not assuming linearity. We will also report the 3-year and 3-year changes (and 95% confidence intervals) predicted by these models. For SRS-QOL and SF-12, component domains will be analyzed both combined and separately as described by Mangione et al.

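### The 80% power for 82 randomised makes no reduction in effect for 20% crossover under intent-to-treat, and the sufficient power claimed for 63 is not shown at the 24-month primary endpoint

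*SAP*

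**What the plan says.** **Analysis and endpoint.** The SAP (Stage 3, Primary Analyses) states: "In the randomized cohort, the primary analysis will be on an intent-to-treat basis". The same paragraph refers to the "12-month and 24-month (primary endpoint) follow-up periods", and section 1.6.2 says the study was powered at two years.

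**82 randomised.** Section 1.6.3 starts from 41 per arm and applies 20% crossover in the non-operative arm and then 10% loss, ending at 36 operative, 30 non-operative and 7 crossovers. It says that intent-to-treat would keep the crossovers where they were assigned, and that 80% power still applies at effect sizes of 0.714 and 0.814 or more. The addendum dated 1/17/13 repeats the claim: "A sample size of 82 patients (41 per treatment arm) was estimated to provide 80% power with an SRS-22 effect size" of 0.714 or more, with 10% loss and "20% crossover from nonoperative to operative intervention".

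**63 enrolled.** The addendum then reports that "a bootstrap sample size estimation using data from the first 26 patients randomized was performed". Its table has rows at 3, 6, 9 and 12 months, for 18 per group. It concludes: "These results suggested that >80% power could be achieved to address Aim #1 with 36 randomized patients (18 patients per group)". Finally, "Enrollment in the randomized cohort closed July 2014 with 63 participants, 70% of the original enrollment goal", which was judged "to allow for sufficient power making allowances for loss to follow-up and cross-over over time".

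**The concern.** Under intent-to-treat, a non-operative patient who has surgery is not removed from the comparison. The patient stays in the non-operative arm and, to the extent that surgery has helped by 24 months, narrows the difference between arms. Crossover is therefore a question about the effect size, and the plan treats it as a question about counts. Naming a 20% crossover rate beside the 80% suggests that the cost has been paid, but no step in the documents pays it.

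For the 63 enrolled, the only analysis printed after the original sizing ends a year before the primary endpoint.

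At stake is how a non-significant 24-month intent-to-treat result would be read. Set against a flat 80%, or against sufficient power for 63, it would look like stronger evidence of no difference than the documented calculations support.

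**Working it through.** **Inputs.** Two-sided alpha 0.05 and power 0.80 (section 1.6.2). Effect sizes 0.5/0.7 = 0.714 and 0.4/0.6 = 0.667 (Table 2; section 1.6.4 names this pair). Crossover 20% and loss 10% (section 1.6.3). The share *s* of the operative benefit that crossovers gain by 24 months is not given, so I use 0, 0.5 and 1 as an assumption.

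**Method.** Two-sample t-test at one time point, noncentral t with noncentrality d × √(n₁n₂/(n₁+n₂)). Intent-to-treat effect = d × (1 − 0.20 × s).

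**Step 1: reproduce the plan.** All six rows of Table 2 reproduce: 24, 37, 64, 32, 50, 87. So does section 1.6.4's 29 per group for 70% power at 0.667 (70.4%). Table 2 is not in question.

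**Step 2: trace the 80% for 82.** With the effect left at 0.714:
- 36 v 30, crossovers left out: 81.2%, which matches the stated figure
- 36 v 37 (30 + 7), crossovers kept as intent-to-treat requires: 85.3%

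**Step 3: allow for dilution, 36 v 37.** The multipliers on the effect are 1, 0.9 and 0.8.

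| Effect | s = 0 | s = 0.5 | s = 1 |
|---|---|---|---|
| 0.714 | 85% | 77% | 67% |
| 0.667 | 80% | 72% | 61% |

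Power falls to 80% at s ≈ 0.35 for 0.714 and at s ≈ 0.01 for 0.667.

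Table 2 itself gives a check. At s = 1 the non-operative mean becomes 0.8 × 0.3 + 0.2 × 0.8 = 0.40, so the effect is (0.8 − 0.4)/0.7 = 0.571. That is a row of Table 2, and it needs 50 per group against about 37 available.

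**Step 4: the 63 enrolled on Table 2 inputs.** 63 × 0.9 = 56.7, taken as 28 v 28 (28 v 29 adds at most 0.01).

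| Effect | s = 0 | s = 0.5 | s = 1 |
|---|---|---|---|
| 0.714 | 75% | 66% | 56% |
| 0.667 | 69% | 60% | 50% |

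Section 1.6.4 sets its futility threshold at 58 patients for power in the 70% range. About 57 retained is one short of that. The undiluted figures lie near 70%, and all six are below 80%.

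**Step 5: what the bootstrap covers.** At 3, 6, 9 and 12 months, SRS power is 0.677, 0.998, 1.000 and 0.995; ODI power is 0.039, 0.727, 0.560 and 0.817. There is no 24-month row, no power figure for 63, and no printed calculation for loss or crossover.

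**Step 6: figures in the same statements that disagree.**
- 0.814 (section 1.6.3) is in no row of Table 2; section 1.6.4 gives .667 to .714.
- Section 1.6.3 puts the 20% crossover in the non-operative arm, then describes the 8 patients as moving from operative to non-operative.
- 63/0.70 = 90, but the addendum's goal is 82 (63/82 = 77%) and section 1.6.4 expects about 100.
- Section 1.6 says the standard deviations ignore shrinkage from baseline covariates; section 1.6.2 says the estimates were adjusted for baseline SRS, age, gender and Cobb angle.

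**The case against.** **0.714 may already be the intent-to-treat effect.** If so, 36 v 37 gives 85% and the claim for 82 holds. No passage says this. On that reading the 20% crossover does no work in the calculation and, with full benefit to crossovers, the undiluted effect would have to be 0.714/0.8 ≈ 0.89.

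**Crossovers may gain little by 24 months.** This stands as a possibility. The treadmill rules in Protocol section 1.5 provide for crossover surgery between 21 and 30 months. It is the reason for giving a range. Against it, the SAP's Evaluating Crossover section also expects patients assigned to surgery who never have it; the sizing omits them, and they would lower power further.

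**Covariates may restore the power.** If Table 2's standard deviations are unadjusted, covariates explaining about 26% of variance would bring 82 back to 80% at 0.714 under full dilution (0.571/√0.74 ≈ 0.66, the effect needed at 36 v 37). If they are already adjusted, that gain has been spent. Sections 1.6 and 1.6.2 disagree on which is so. Section 1.6 also says that repeated assessments do not add power to these between-group tests, while section 1.6.3 expects some added precision from them.

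**The bootstrap supports 63.** Much of this stands. SRS-QOL is the primary outcome, and its bootstrap power is at least 0.995 from 6 to 12 months with 18 per group, which suggests a larger early effect than Table 2 assumes. ODI is secondary, so its weaker rows do not bear on primary power. The margin from 36 to 63 is also reasonable on the bootstrap's own terms: 36/(0.8² × 0.9) = 62.5, although the addendum does not print that step. Crossovers among the first 26 may already be in the data, so diluting again could double-count. What remains unshown is that a 12-month effect from 26 patients lasts to 24 months.

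**A reader might infer that the trial was underpowered, or that 63 had no two-year basis at all.** The documents support neither. The bootstrap points to a larger effect, and section 1.6.4's threshold of 58 rests on the same Table 2 basis that section 1.6.2 ties to two years.

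**Conclusion.** The concern holds as a gap in stated support, not as an error in Table 2. The flat 80% for 82 is true at 0.714 only if crossovers gain less than about 0.35 of the operative benefit by 24 months, or if 0.714 is already the intent-to-treat effect; the plan states neither condition. At 0.667 there is almost no reserve. For 63, the printed evidence for sufficiency stops at 12 months. On Table 2 inputs, 24-month power is 50% to 75% across the two effect sizes and the range of dilution, and the addendum does not say whether sufficient means 80% or the 70% used in section 1.6.4.

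These figures assume a single-time-point t-test (Table 2's basis), 20% crossover in one direction, 10% loss, and a share gained between none and all. I give no back-calculated effect or persistence percentage from the bootstrap. It uses 26 patients, its SRS power is near 1 where power hardly changes with effect size, and one ODI value (0.039) is below what any effect would give in a two-sided 0.05 t-test.

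**What to change.** **Section 1.6.3 and the addendum, 82 randomised.** Replace the flat 80% with, for example: *Under intent-to-treat (36 v 37 after 10% loss, 20% non-operative-to-operative crossover), two-sample t-test power at 24 months is 85%, 77% or 67% at effect size 0.714, and 80%, 72% or 61% at 0.667, if crossovers gain none, half or all of the operative benefit by then; this share is an assumption.* If 0.714 was meant as the intent-to-treat effect, say so instead. Add that operative-to-non-operative crossover is not in the sizing and would lower power further; the documents give no rate, so none should be fixed here.

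**Addendum, 63 enrolled.** State that the bootstrap covers up to 12 months only and that persistence to 24 months is not shown. Give the Table 2-based range (75/66/56% at 0.714, 69/60/50% at 0.667), and say whether sufficient refers to 80% or to section 1.6.4's 70%.

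**Reconcile:**
- 0.814 with Table 2 and section 1.6.4. Putting 0.667 in its place while keeping 80% would not do: 36 v 30 gives 76% there, and 36 v 37 only just reaches 80% with no dilution.
- The direction of crossover in section 1.6.3.
- The randomised enrolment goal: 82, the 90 implied by 70%, or about 100.
- Sections 1.6 and 1.6.2 on covariate adjustment.

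**Cost.** SAP wording only. There are no extra patients and no change to the analysis; the stated power becomes less favourable.
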